Proprietary confidential information © 2022 Boehringer Ingelheim International GmbH or one or more of its affiliated companies

In order to protect the patient's safety during conduct of this trial, an independent Data Monitoring Committee has been established for the periodic review of clinical trial safety data.

Table 1.4:1 Benefit – Risk Assessment

Hypothetical risks of clinical relevance for this trial	Summary of data, rationale for the risk	Mitigation strategy
Investigational Medicinal Product		
Drug-induced liver injury (DILI)	Rare but severe event, thus under constant surveillance by sponsors and regulators.	Timely detection, evaluation, and follow-up of laboratory alterations in selected liver laboratory parameters to ensure patients' safety. See also Section 5.2.6 , adverse events of special interest
Systemic hypersensitivity reaction	After administration of any biologic agent or protein, there is a possibility of occurrence of adverse immune reactions which can be local (e.g redness, pruritus, and or swelling at the injection site) or systemic (e.g. anaphylactic reactions).	Patients with a history of allergy/ hypersensitivity to the systemically administered trial medication agent or its excipients are excluded from the trial. In case of systemic hypersensitivity reactions including anaphylactic reaction emerging during or after administration of trial medication, the investigator should consider in accordance with severity of the reaction and local standard of care to interrupt and treat the condition. Systemic hypersensitivity reaction is defined as AESI. It is subject to close monitoring and investigators are requested assess these conditions using the criteria discussed in the statement paper from Sampson HA [R11-4890].

Table 1.4:1

Benefit – Risk Assessment (cont.)

Investigational Medicinal Product		

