4.1.4 Drug assignment and administration of doses for each patient

In this trial a dose of 300 mg of BI 655130 (SPESOLIMAB) will be administered during study visit as subcutaneous injection in the abdomen, in accordance with local standard

procedure and as described in “BI 655130 Solution for Injection 150 mg/mL s.c. Instructions for Handling and Use”

every 4 weeks for patients starting from visit M1 until EOT visit for patients who responded to treatment with study drug in previous trials or gained response after i.v. re-induction period. The concentration of the application solution will be 150 mg/ml.

Injection site should not be close to a vein and it should avoid sites where the skin is tender, bruised, erythematous, or indurated, and should be alternated to other areas for subsequent doses.

Detailed instructions for Handling and Use of s.c. injection are provided in the ISF.

Patients have to be closely monitored for local or systemic hypersensitivity reactions for 1 hour following s.c. study drug administration. Subcutaneous administration of biologic agents involves the risk of local (injection site) or systemic hypersensitivity reactions. Therefore, patients should be closely monitored for signs and symptoms of injection site or systemic hypersensitivity reactions following study drug administration. Study personnel should observe the injection site for signs of redness, swelling or hardness. They should also ask subjects about itching, dizziness or shortness of breath. Patients should be advised that if they experience redness, swelling or other changes at the injection site, they should notify site personnel. They should further be advised that if they experience itching all over or a feeling of being swollen, dizzy or short of breath, they should seek emergency medical attention immediately and notify site personnel.

1200mg BI 655130 (SPESOLIMAB) i.v. q4w administration for 12 weeks will be used for patients assigned to i.v. re-induction.

Single 1200 mg BI 655130 (SPESOLIMAB) i.v. administration will be used as disease flare treatment. Intravenous infusion including observational time for possible infusion reactions will last approximately 2.5 hours. The i.v. treatment will be followed by intensified maintenance treatment with 600mg BI 655130 (SPESOLIMAB) q6w.

Detailed instructions for the preparation of the i.v. infusion solution, the volume to be administered and the infusion rate are provided in the ISF.

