4.2 OTHER TREATMENTS, EMERGENCY PROCEDURES, RESTRICTIONS

4.2.1 Other treatments and emergency procedures

If the patient requires additional medical therapy or dose increase of baseline ulcerative colitis medication (other than BI 655130 (SPESOLIMAB) to treat a disease flare or a reversion to the preceding higher daily steroid dose during tapering of steroids) to treat the underlying ulcerative colitis due to disease worsening (cf. [Table 2.1:1](#) Definition of Study Outcomes), the study drug must be discontinued and patients may receive conventional treatment for active disease. In case of disease flare during maintenance treatment period, patient must be provided with disease flare treatment (single i.v. dose of 1200 mg BI 655130 (SPESOLIMAB) infusion) followed by intensified maintenance treatment with 600mg BI 655130 (SPESOLIMAB) q6w.

In case of undue safety risk for the subject, the subject should discontinue study treatment at the discretion of the investigator. If the subject receives a live virus vaccination during the study, the subject must discontinue study treatment.

Systemic steroids dosed intravenously or orally for less than 24 hours as treatment of infusion or anaphylactic reactions are permitted and do not lead to treatment discontinuation (see [Table 4.2.2: 1](#)).

If mild-to-moderate infusion or anaphylactic reaction had already occurred in the very same patient in the past, pre-treatment with steroids before next IMP administration is permitted as secondary prophylaxis.

Locally administered steroids as e.g. intraarticular, nasal inhalation or intraocular administration are allowed, but their application has to be carefully monitored and reported in CRF (see [Table 4.2.2: 1](#)).

Management of Adverse Events:

Infusion reactions / Systemic hypersensitivity including anaphylactic reaction

In case of infusion reactions / systemic hypersensitivity including anaphylactic reaction emerging during or after infusion / injection(s) of study drug, the investigator should consider in accordance with severity of the reaction and local standard of care to:

- Immediately interrupt the infusion / Stop further injections
- Treat with systemic anti-histamines, intravenous steroids, and in case of a severe allergic reaction (e.g., anaphylactic reaction) epinephrine

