The latest list of “Always Serious AEs” can be found in the eDC system. A copy of the latest list of “Always Serious AEs” will be provided upon request. These events should always be reported as SAEs as described above.

Adverse Events of Special Interest (AESIs)

The term AESI relates to any specific AE that has been identified at the project level as being of particular interest or prospective safety monitoring and safety assessment within this trial. AESIs need to be reported to the sponsor’s Pharmacovigilance Department within the same timeframe that applies to SAEs, please see above.

The following are considered as AESIs:

- Systemic hypersensitivity including infusion reaction and anaphylactic reaction

Any suspicion of severe infusion reaction and of any potential cases of anaphylaxis should be defined and assessed using the criteria discussed in the statement paper from Sampson HA ([Appendix 10.5, R11-4890](#)).

Severe infections (according to (according to RCTC grading in Appendix 10.6)

Opportunistic and mycobacterium tuberculosis infections

These include pneumocystis jirovecii, BK virus disease including PVAN, CMV, post-transplant lymphoproliferative disorder (EBV), progressive multifocal leucoencephalopathy, bartonellosis (disseminated only), blastomycosis, toxoplasmosis, coccidioidomycosis, histoplasmosis, aspergillosis (invasive only), candidiasis (invasive or pharyngeal), cryptococcosis, other invasive fungi (mucormycosis (zygomycosis, rhizopus, mucor, lichtheimia), scedosporium/pseudallescheria boydii, fusarium), legionellosis, listeria monocytogenes (invasive only), tuberculosis, nocardiosis, non-tuberculous mycobacterium, salmonellosis (invasive only), HBV reactivation, herpes simplex (invasive only), herpes zoster, strongyloides (hyperinfection syndrome and disseminated forms only), paracoccidioides, penicillium marneffei, sporothrix schenckii, cryptosporidium species

(chronic only), microsporidiosis, leishmaniasis (visceral only), trypanosoma cruzi infection (Chagas' disease) (disseminated only), campylobacteriosis (invasive only), shigellosis (invasive only), vibriosis (invasive due to vibrio vulnificus), HCV progression [[R17-2617](#)]

Hepatic injury

A hepatic injury is defined by the following alterations of hepatic laboratory parameters:

- a. ALT or AST >5x ULN
- b. ALT or AST >3x ULN with the appearance of fatigue, nausea, vomiting, right upper quadrant pain or tenderness, fever, rash, and/or eosinophilia (> 5%)

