- c. AST and/or ALT >3 fold ULN combined with an elevation of total bilirubin >2 fold ULN measured in the same blood draw sample

These lab findings constitute a hepatic injury alert and the patients showing these lab abnormalities need to be followed up according to the "DILI checklist" provided in the ISF.

In case of clinical symptoms of hepatic injury (icterus, unexplained encephalopathy, unexplained coagulopathy, right upper quadrant abdominal pain, etc.) without lab results (ALT, AST, total bilirubin) available, the investigator should make sure these parameters are analysed, if necessary in an unscheduled blood test. Should the results meet the criteria of hepatic injury alert, the procedures described in the DILI checklist should be followed.

If an alternative cause for the hepatic injury cannot be identified in the follow-up assessments specified in the "DILI checklist", discontinuation of treatment with study drug should be considered.

Peripheral Neuropathy

Any event suspected or diagnosed as Peripheral Neuropathy would be considered as an AESI. For the treatment interruption rules, please see [section 3.3.4.1](#)

Intensity (severity) of AEs

The intensity grading of AEs will be performed according to Rheumatology Common Toxicity Criteria (RCTC) Version 2.0 developed by [REDACTED] ([Appendix 10.6, R13-3515](#)). Refer to the ISF for intensity/severity classification. Intensity options are:

Grade 1	mild
Grade 2	moderate
Grade 3	severe
Grade 4	life-threatening

Causal relationship of AEs

Medical judgement should be used to determine the relationship, considering all relevant factors, including pattern of reaction, temporal relationship, de-challenge or re-challenge, confounding factors such as concomitant medication, concomitant diseases and relevant history.

Arguments that may suggest that there is a reasonable possibility of a causal relationship could be:

- The event is consistent with the known pharmacology of the drug.
- The event is known to be caused by or attributed to the drug class.
- A plausible time to onset of the event relative to the time of drug exposure.
- Evidence that the event is reproducible when the drug is re-introduced
- No medically sound alternative aetiologies that could explain the event (e.g. pre-existing or concomitant diseases, or co-medications).
- The event is typically drug-related and infrequent in the general population not exposed to drugs (e.g. Stevens-Johnson syndrome).

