#### **4. CHANGES IN THE PLANNED ANALYSIS OF THE STUDY**

The population label for Treated Set (TS) is updated to be Safety Analysis set (SAF) based on current project definition. Thus the TS-RT for re-induction treatment becomes SAF-RT, and TS-MT for maintenance treatments becomes SAF-MT.

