For safety analysis on the disease flare treatment period: Time at risk [subject years] = (date of onset of AE – prior i.v. disease flare treatment start date + 1) / 365.25

- 3) If, for a subject, the selected treatment emergent adverse event didn't occur then the time at risk will be censored at min (date of death, date of end of applicable treatment period per [Section 6.1](#), or date of cut-off if interim analysis performed). For each selected treatment emergent AE, the exposure adjusted incidence rate will be calculated as:
- 4) Incidence rate [1/100 Subject years (pt-yrs)] = 100 \* number of subjects with TEAE / Total TEAE-specific time at risk [subject years].

An overall summary of AEs will be presented. This overall summary will include summary statistics for the class of other significant AEs derived according to an adaptation of the ICH E3 ([6](#)) and for the class of AESIs.

The following are considered as AESIs (cf. CTP section 5.2.6.1):

- Infusion reactions including anaphylactic reaction
- Severe infections (according to RCTC grading)
- Opportunistic and mycobacterium tuberculosis infections
- Hepatic injury

*A hepatic injury is defined by the following alterations of hepatic laboratory parameters:*

- a. ALT or AST >5x ULN*
- b. ALT or AST >3x ULN with the appearance of fatigue, nausea, vomiting, right upper quadrant pain or tenderness, fever, rash, and/or eosinophilia (> 5%)*
- c. AST and/or ALT ≥3 fold ULN combined with an elevation of total bilirubin ≥2 fold ULN measured in the same blood draw sample*

The investigator identified AESI will be captured from the eCRF and reported in the “Investigator reported AESI” table. In addition, user defined adverse event concepts (UDAEC) identified through specific search criteria will be reported separately ([Table 7.8.1: 1](#)).

Adverse Events classified as ‘other significant’ will be reported using an adaptation of the ICH E3 ([6](#)) and will include those non-serious and non-significant AEs which were reported with ‘action taken = drug withdrawn’ or ‘action taken = reduced’.

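### The SAP's list of adverse events of special interest omits peripheral neuropathy and narrows systemic hypersensitivity to infusion reactions, contrary to the protocol section it cites

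*SAP*

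**What the plan says.** SAP section 7.8.1 promises an overall adverse event summary that includes statistics for the AESI class. It then defines the class with the words "The following are considered as AESIs (cf. CTP section 5.2.6.1" and lists four items. The first is "Infusion reactions including anaphylactic reaction"; the others are severe infections, opportunistic and tuberculosis infections, and hepatic injury. The section also announces a separate table of patients with AESIs, a table of investigator-reported AESIs taken from the eCRF, and a separate report of user-defined adverse event concepts (UDAECs) found by search criteria.

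Protocol section 5.2.6.1 (version 8.0) lists five categories. Its first is "Systemic hypersensitivity including infusion reaction and anaphylactic reaction", and the benefit-risk table in section 1.4 confirms the parent term: "Systemic hypersensitivity reaction is defined as AESI". Its last is peripheral neuropathy: "Any event suspected or diagnosed as Peripheral Neuropathy would be considered as an AESI".

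SAP section 4, which records changes to the planned analysis, has one entry, a relabelling of analysis sets: "The population label for Treated Set (TS) is updated to be Safety Analysis set (SAF) based on current project definition".

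**The concern.** The SAP cites the protocol section as the source of its AESI list and then gives a different list. Two of the differences could lose a case. One protocol category is absent, and another has lost its parent term and kept only two of its members.

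Long-term safety is the first of the trial's two main objectives, and an AESI display exists to bring together events that might otherwise be scattered across preferred terms. Neuropathy is a specific concern in this programme. Protocol section 1.4 describes three cases in spesolimab trials that investigators reported as Guillain-Barré syndrome. An external panel thought the findings in all three were best described as peripheral neuropathy and noted that the pattern varied. If the AESI line or table is programmed from the SAP list, such events could be missing from the display designed to show them.

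**Working it through.** No figure in the plan needs reproducing, because the trial is descriptive and the point is a comparison of two lists. The inputs are protocol section 5.2.6.1 and SAP section 7.8.1.

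| Protocol 5.2.6.1 | SAP 7.8.1 | Result |
|---|---|---|
| Systemic hypersensitivity, with infusion and anaphylactic reactions as members | Infusion reactions, with anaphylactic reaction | Narrowed; a case could be lost |
| Severe infections (RCTC grade) | Same | Match |
| Opportunistic and tuberculosis infections | Same | Match |
| Hepatic injury, criterion c: >3× and >2× ULN | Hepatic injury, criterion c: ≥3× and ≥2× ULN | Differs; SAP is wider, no case lost |
| Peripheral neuropathy, suspected or diagnosed | Not listed | Absent; a case could be lost |

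**Count.** Match 2, differ without loss 1, possible loss 2; 2 + 1 + 2 = 5 protocol categories.

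**Does the narrowing matter for the route used?** Maintenance dosing is subcutaneous. Protocol section 4.1.4 states: "Subcutaneous administration of biologic agents involves the risk of local (injection site) or systemic hypersensitivity reactions". Section 4.2.1 gives its instructions for both routes: "In case of infusion reactions / systemic hypersensitivity including anaphylactic reaction emerging during or after infusion / injection(s) of study drug". A systemic reaction to an injection that does not meet the anaphylaxis criteria is therefore an AESI under the protocol. Taken literally, it is neither an infusion reaction nor an anaphylactic reaction, so it falls outside the SAP list.

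**Is the difference declared?** SAP section 4 mentions neither category.

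**Timing.** The last SAP version in the history table is 4.0 of 13 January 2021; the protocol is version 8.0 of 23 May 2022. The gap is 365 days to 13 January 2022 plus 130 days to 23 May 2022, or 495 days. This describes the age of the SAP and says nothing about how many events might be missed.

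**Which displays are exposed?** SAP 7.8.1 states an eCRF source only for the investigator-reported AESI table. It gives none for the AESI line in the overall summary or for the table of patients with AESIs, although the latter may be the same table.

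**The case against.** The strongest reply is that the list only restates the protocol and is not a derivation rule. Apart from the hepatic laboratory limits and the RCTC grade, its items carry no MedDRA terms or search rule. The only sources that SAP 7.8.1 names are the eCRF flag and the UDAEC searches. Investigators flag events under the protocol in force, and protocol section 5.2.6.2 requires all AESIs to be documented on the CRF. This stands as a limit on the consequence: flagged events would still be tabulated. It does not settle the source for the summary line, and it does not make the stated definition correct.

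Second, the sponsor uses the term infusion reaction loosely. Protocol section 6.2.2 speaks of monitoring for infusion reactions after study drug administration without restricting this to the intravenous route, and section 5.2.5 gives infusion-reaction instructions in its paragraph on injection-site tolerability. An intent to exclude injection reactions is therefore unlikely, and none is alleged. The wording still departs from the protocol's parent term.

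Third, the neuropathy gap is probably version lag. The text reviewed does not show which amendment added that category, so the silence of SAP section 4 may not be a fault on this item. Lag explains the gap but leaves the list uncorrected.

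Fourth, UDAEC Table 7.8.1: 1 was not in the text reviewed and may contain searches for either category. That cannot be judged, and its absence is not held against the plan. UDAECs are in any case reported separately and do not define the AESI class.

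**Conclusion.** The concern holds: the SAP definition is wrong as written, because it contradicts the section it cites. On a literal reading, two of five protocol categories could lose cases from an AESI display built from the list. A third differs without loss, and two match. The mismatch is certain on the text; an actual loss of events is only possible. It would require a display to be derived from the SAP list instead of from the eCRF flag, and the number of events cannot be derived from the documents.

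The primary endpoint (any treatment-emergent adverse event) and the tables by system organ class and preferred term are unaffected. The hepatic signs are a secondary inconsistency and should be checked in the original files, since text extraction may have altered them. The SAP should be corrected, but the point does not threaten the trial's main result.

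**What to change.** 1. Replace the AESI list in SAP 7.8.1 with the five categories of protocol 5.2.6.1, version 8.0, restoring systemic hypersensitivity as the parent term and adding peripheral neuropathy.
2. Add one sentence stating that the AESI line in the overall summary and the table of patients with AESIs use the same protocol-defined, eCRF-identified class as the investigator-reported AESI table.
3. Reconcile the inequality signs in hepatic criterion c between the two documents.

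A MedDRA search for neuropathy, if the UDAEC table does not already include one, may be reported separately as a UDAEC and need not be merged into the AESI class.

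The cost is a text edit: one list, one sentence and the signs in one criterion. No new data collection is involved, and no new search is required.

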3.3.4 Withdrawal of patients from therapy or assessments

Patients may potentially be withdrawn from trial treatment or from the trial as a whole (“withdrawal of consent”) with very different implications, please see [sections 3.3.4.1](#) and [3.3.4.2](#) below.

The decision to withdraw from trial treatment or from the whole trial as well as the reason must be documented in the patient files and CRF.

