3.3.4.1 Withdrawal from trial treatment

An individual patient is to be withdrawn from trial treatment if:

- A patient assigned to re-induction treatment does not achieve clinical response at week 12 compared to baseline of the original induction trial.
- A patient treated for a disease flare does not achieve clinical response (compared to baseline of the original induction trial) or clinical remission within 12 weeks after the initiation of disease flare treatment.
- A patient experience more than 1 confirmed flares during the trial.
- The patient wants to withdraw from trial treatment, without the need to justify the decision.
- The patient needs to take concomitant drugs that interfere with the investigational product. Please refer to [section 4.2.1](#) and [4.2.2](#).
- The patient can no longer be treated with trial medication for other medical reasons (such as surgery, adverse events, other diseases, or pregnancy).
- The patient has repeatedly shown to be non-compliant with important trial procedures and, in the opinion of both, the investigator and sponsor representative, is not willing or able to comply with the trial requirements in the future.
- A patient can be discontinued from trial medication at any time if in the opinion of the Investigator, continuation with trial medication is not in the patient’s best interest.
- For individual stopping rules related to specific adverse events, please see [section 4.2.1](#) “Other treatments and emergency procedures”.
- If peripheral neuropathy is suspected, treatment with spesolimab should be temporarily discontinued until a full neurological investigation has been conducted. After completion of the neurological investigation, treatment can be restarted based on medical judgement of the investigator.

Proprietary confidential information © 2022 Boehringer Ingelheim International GmbH or one or more of its affiliated companies

If a patient has not achieved clinical remission within the first 48 weeks of maintenance treatment, investigator should consider trial drug termination based on individual patient history and available alternative treatment options.

Given the patient's agreement, the patient will undergo the procedures for early treatment discontinuation and follow up as outlined in the [Flow Charts](#) and [section 6.2.3](#).

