6.2.3.1 Early treatment discontinuation

Patient who discontinue treatment prior to the planned EOT visit have to be invited for an early EOT visit as soon as possible. These patients should be registered as withdrawn from treatment in IRT and return to the site for the End of Study (EOS) visit 16 weeks after last study drug intake.

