6.2.3.2 Trial completion

Patients who finish the treatment period will return to the site for the End of Study (EOS) visit 16 weeks after the EOT visit. Completion is defined as a patient having reached the EOS visit.

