### 6.6.1      **Withdrawals**

The reasons for withdrawal from treatment will be reported as indicated on the eCRF.

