## 7. PLANNED ANALYSIS

### *General Remarks*

The format of the listings and tables will follow the BI guideline "Reporting of clinical trials and project summaries" (001-MCG-159) ([7](#)).

The individual values of all patients will be listed, including those collected during the off-treatment period. Listings will generally be sorted by country, centre number, patient number and visit (if visit is applicable in the respective listing). (see [Section 7.8.1](#) below for details).

The following standard descriptive statistical parameters will be displayed in summary tables of continuous variables:

N	number of non-missing observations
Mean	arithmetic mean
SD	standard deviation
Min	minimum
Q1	lower quartile
Median	median
Q3	upper quartile
Max	maximum

Statistical parameters will be displayed to a defined number of decimal places as specified in the BI guideline "Reporting of clinical trials and project summaries" ([7](#)).

Tabulations of frequencies for categorical data will include all possible categories and will display the number of observations in a category as well as the percentage (%) relative to the respective patient set (unless otherwise specified, all patients in the patient set irrespective of whether they have non-missing values or not). Percentages will be rounded to one decimal place. The category missing will be displayed only if there are actually missing values.

Disposition of the patient population for each trial part (re-induction or overall maintenance) will be summarised by presentation of the frequency of patients enrolled, treated, enrolled but not treated, who completed all doses of trial medication as planned, who completed the PE visit (EOT), who completed the trial (EOS), and who were prematurely discontinued, by reason. Additional summaries by the parent trial will be produced, and, summaries of the maintenance period disposition according to whether or not a patient experienced re-induction treatment or not will also be done. The frequency of patients with iPDs will also be presented; the iPDs will be listed per patient.

To better illustrate the long-term efficacy of the overall maintenance treatment (defined in [Table 6.1: 4](#)), a summary table regarding patient status over time will be added. The cumulative frequency of patients for the following categories will be displayed based on 12-week interval:

- ongoing on study medication, i.e., without early treatment discontinuation by the time point

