The exposure-adjusted incidence rate and frequency of patients with AEs will be summarised by treatment, primary system organ class and preferred term. AEs which were considered by the investigator to be drug related will be summarised separately. Separate tables will also be provided for patients with SAEs, patients with AESIs, patients with AE leading to discontinuation of the trial, patients with other significant AEs and User-defined Adverse Event Concepts (UDAEC) (see [Table 7.8.1: 1](#)). AEs will also be summarized by maximum intensity based on the RCTC measure (see [Section 5.4.1](#)).”

For disclosure of AE data on ClinicalTrials.gov, the frequency of patients with non-serious AEs occurring with an incidence of greater than 5% (in preferred terms) will be summarised by primary system organ class and preferred term. The frequency of patients with SAEs will also be summarised.

For disclosure of AE data in the EudraCT register, the frequency of non-serious AEs with an incidence of greater than 5% (in preferred terms) and the frequency of SAEs will be summarised.

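### SAP 7.8.1 keys its AE discontinuation table to leaving the trial, not stopping drug, so a serious AE that ended treatment in a patient who attended EOS is identified in no named discontinuation table

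*SAP*

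**What the plan says.** SAP 7.8.1 lists the AE tables to be produced apart from the main summaries: drug-related AEs, SAEs, AESIs, "patients with AE leading to discontinuation of the trial, patients with other significant AEs", and user-defined AE concepts. No table of AEs leading to discontinuation of trial drug is named.

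The same section defines the other significant class: it "will include those non-serious and non-significant AEs which were reported with" drug withdrawn or dose reduced as the action taken.

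The protocol treats stopping drug and leaving the trial as different events. Section 3.3.4 opens: "Patients may potentially be withdrawn from trial treatment or from the trial as a whole", and equates the second with withdrawal of consent. Adverse events are listed in section 3.3.4.1 among the reasons for stopping treatment: "The patient can no longer be treated with trial medication for other medical reasons (such as surgery, adverse events, other diseases, or pregnancy". Under section 6.2.3.1, patients who stop early have an early EOT visit and then "return to the site for the End of Study (EOS) visit 16 weeks after last study drug intake". Section 6.2.3.2 adds: "Completion is defined as a patient having reached the EOS visit".

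For disposition, SAP section 7 (General Remarks) counts patients "who completed the trial (EOS), and who were prematurely discontinued, by reason". SAP 6.6.1 states: "The reasons for withdrawal from treatment will be reported as indicated on the eCRF".

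**The concern.** In a long-term safety trial, the AEs that made patients stop drug are a main tolerability result, and a reader will look for them in the table of AEs leading to discontinuation. If that table is built on discontinuation of the trial, a patient who stops drug for an AE and is then followed as planned may not enter it. The other significant table recovers non-serious events of this kind but excludes serious ones by definition. The result could be a discontinuation table that leaves out serious events that ended treatment and that does not reconcile with the reasons for treatment withdrawal reported under SAP 6.6.1.

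**Working it through.** There is no figure to reproduce; the trial is descriptive. The check is to take each kind of AE that ends treatment and see which tables named in SAP 7.8.1 would hold it.

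**Inputs**

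- Discontinuation table: defined by discontinuation of the trial (SAP 7.8.1).
- Other significant table: drug withdrawn or reduced, non-serious and non-significant events only (SAP 7.8.1).
- Trial completion: reaching EOS (protocol 6.2.3.2). SAP section 7 also ties trial completion to EOS.
- Route after an early stop: EOT, then EOS 16 weeks after the last dose (protocol 6.2.3.1).

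**Tracing the cases on the SAP's wording**

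| AE that ended treatment | EOS reached? | SAE table | Other significant table | Discontinuation-of-trial table |
|---|---|---|---|---|
| 1. Non-serious, not otherwise significant | Yes | No | Yes | No |
| 2. Serious | Yes | Yes | No (serious) | No, if reaching EOS means completion |
| 3. Serious, and the AE prevents EOS (including death) | No | Yes | No | Yes |
| 4. Non-serious AESI | Yes | No (in the AESI table) | Unclear: the SAP does not define significant | No, if reaching EOS means completion |

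Case 2 is the gap. Case 4 may be a second, smaller one.

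**Is case 2 foreseeable?** Yes, for malignancy. Protocol 4.2.1 has the investigator discontinue study drug for a malignancy, with stated exceptions. Protocol Table 1.4:1 and section 5.2.6.1 make cancers serious in every case. Such an event can never be in the other significant table, and it enters the discontinuation table only if the patient does not reach EOS. Infection and suspected neuropathy are weaker examples: protocol 4.2.1 and 3.3.4.1 first describe a pause with possible restart, so they count only when drug is stopped for good.

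**Do other outputs identify the event?**

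- The SAE table shows the event, but the SAP does not say that it will show whether drug was stopped.
- The disposition table and SAP 6.6.1 give patient counts by reason, with no preferred term or seriousness specified.
- The patient-status table in SAP section 7 breaks down stopped medication by flare, rescue medication and death. It has no AE category.
- Individual listings will hold the event, but they are not a summary.

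No named summary therefore says which serious AEs ended treatment in patients who attended EOS.

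**The case against.** The strongest reply is that the phrase is a slip for trial drug. The only AE-level field that the SAP names for stopping is the action taken, and it names none for leaving the trial. Since the protocol equates leaving the trial with withdrawal of consent, for which no reason is required, a table built literally on that would have little to draw on. This is a fair reading of the intent. It does not remove the need to correct the text, because elsewhere the SAP does separate study medication from the trial, and protocol Table 2.1:1 speaks of an AE leading to discontinuation of study drug.

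Second, the list may not be complete. SAP 7.8.1 refers to a sponsor standard for AE summaries, and protocol 7.3.4 promises the sponsor's standard tables. A drug-discontinuation table may come from there. This stands as a limit: the gap can be shown for the tables named in the SAP, not for everything that will be produced.

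Third, the completion sentence in protocol 6.2.3.2 follows one about patients who finish treatment, and early stoppers have their own section, which does not call them completers. That also stands. The status of an early stopper who attends EOS is an inference, supported by the general wording of that sentence and by the SAP's disposition categories.

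Fourth, the number of patients who stop drug for an AE is planned output. Protocol 3.3.4.1 requires the reason to be recorded and reported, and SAP 6.6.1 carries this through. A reader might infer that such patients or events disappear from the report, or that the overall count of AE-driven stops will be understated. The documents do not support that.

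**Conclusion.** The point holds in a narrow form. On the SAP's wording, a serious AE that ended treatment in a patient who attended EOS is reported as an SAE, and the patient is counted among the withdrawal reasons. The event is not identified by system organ class and preferred term in any named table of AEs leading to drug discontinuation. This rests on two assumptions: that the phrase is applied literally, and that an early stopper who attends EOS is not counted as having discontinued the trial.

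No size can be given. A reader might try to infer one by assuming that 70% to 95% of patients who stop for an AE attend EOS and calling that the missed share. For 10 such stops, 10 × (1 − 0.70) = 3 and 10 × (1 − 0.95) = 0.5 would remain in the table. That only restates the assumption. The documents give neither the attendance rate nor the number of stops, and the sum includes non-serious events that the other significant table would show.

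The primary endpoint and trial conduct are not affected. The correction is still worth making, because the rule as written points a tolerability table of a safety trial at the wrong event.

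**What to change.** In SAP 7.8.1, replace the reference to AEs leading to discontinuation of the trial with: *AE leading to discontinuation of trial medication (action taken = drug withdrawn), serious and non-serious*, by system organ class and preferred term, for each treatment period. Keep other significant AEs as the non-serious subset. If wanted, show discontinuation of the trial due to an AE as a separate row.

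The action-taken field already named in the SAP supplies the data, so nothing new is collected. The cost is one phrase, one more standard table, and a discontinuation count that may be less favourable.
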